6.4 DISPOSITION AND STUDY PARTICIPATION

A disposition listing will present date and time of informed consent, date of study completion or early withdrawal, and the reason for early discontinuation.

The number of subjects that completed, number of subjects that discontinued and the main reasons for early withdrawal will be summarised by dose group. Dose group assignment and IP administration will be presented for individual subjects in a data listing.

All available information concerning major protocol deviations, violations on eligibility criteria, exclusion from analysis sets and subjects not treated will be listed. The number of subjects in each analysis set will be tabulated.

6.5 DEMOGRAPHIC AND BASELINE DATA

Individual subject demographics at screening (age, sex, race, height, weight and BMI), serology and special tests, red cell alloantibody, urine drug screen results, alcohol breath test results, G6PD status, pregnancy and FSH test results, and the Beck Depression Inventory will be presented in data listings.

Subject age, height, weight, and BMI will be summarised by treatment using descriptive statistics. Sex and race will be summarised using frequency counts and percentages.

6.6 MEDICAL HISTORY

Medical history findings are coded using the Medical Dictionary for Regulatory Activities (MedDRA) into system organ classes and preferred terms. For each finding, a start and stop date or ongoing flag is collected.

Medical history will be tabulated as below:

- The number and percentage of subjects with and without findings

	STATISTICAL ANALYSIS PLAN	QP17C19
		Page 20 of 53

- The number and percentage of subjects with findings by system organ class and preferred term

All medical history data will be listed.

6.7 STUDY MEDICATION/COMPLIANCE

Individual records of drug name, dose levels, date and time of challenge agent administration, IP administration and rescue medication administration will be presented in data listings.

6.8 SAFETY DATA

Adverse events

Adverse events (AEs) and AESIs will be coded using the most current Medical Dictionary for Regulatory Activities (MedDRA®) available at CNS (21.0). Listings of AEs, as well as the severity, relationship, duration, outcome, actions taken, and whether the AE was treatment-emergent and/or an SAE will be presented for each subject. Treatment-emergent adverse events (TEAEs) will be defined as any AE with an onset after administration of study drug, or any AE that has worsened after administration of study drug.

An AESI (serious or non-serious) is one of scientific and medical concern specific to the Sponsor's product or programme, for which ongoing monitoring and rapid communication by the Investigator to the Sponsor could be appropriate. Any abnormalities listed below should be reported as AESI:

Hepatic:

- any ALT or AST above 5xULN
- an elevation in bilirubin 2xULN
- any AST or ALT above 2xULN and (TBL > 1.5x ULN or INR > 1.4)
- any AST or ALT above 2xULN with the appearance of fatigue, nausea, vomiting, right upper quadrant pain or tenderness, fever, rash and/or eosinophilia (eosinophil percent or count above the ULN)

	
STATISTICAL ANALYSIS PLAN
	
QP17C19

		
Page 21 of 53

Cardiac:

- QTcB or QTcF at any time >480 msec,
- bundle branch block (except right bundle branch block that was present prior to IP administration)

any arrhythmia, except:

- sinus bradycardia that is
 - clinically asymptomatic, and
 - not associated with any other relevant ECG abnormalities
- sinus tachycardia that is
 - clinically asymptomatic, and
 - associated with a body temperature >38.0 °C, and
 - not associated with any other relevant ECG abnormalities

respiratory sinus arrhythmia,

wandering atrial pacemaker,

isolated, single premature atrial/ventricular complex (i.e. no bigeminy, trigeminy, couplets, triplets or salvos) that does not occur more than once in a particular ECG tracing.

Haematological:

HB drop >2.0 g/dL from baseline prior to inoculation

Absolute neutrophil count <500/µl.

Platelet count <75,000 /mm³

Dermatological:

Clinical signs of possible cutaneous adverse reactions such as:

- dermatitis,
- rash,
- erythematous rash,
- macular rash,
- papular rash,
- maculopapular rash,
- pruritic rash,
- pustular rash,
- vesicular rash.

Data for AEs for each subject will be presented in data listings. A listing of deaths, other serious and significant AEs, as well as AESIs, will also be presented.

All AEs and AESIs will be summarised in tables. An overview table will show the number and percentage of subjects with at least one event and the number of events for the following:

- TEAEs
- Serious TEAEs
- Fatal TEAEs

	STATISTICAL ANALYSIS PLAN	QP17C19
		Page 22 of 53

- Treatment-related TEAEs
- TEAEs related to IBSM inoculum
- TEAEs related to procedure
- TEAEs related to rescue drug
- Serious treatment-related TEAEs
- TEAEs for which the study was discontinued
- TEAEs for which the study drug was discontinued
- TEAEs of special interest

Summary tables by MedDRA system organ class and preferred term will show the number and percentage of subjects with at least one event. The table of TEAEs will additionally show the number of events. Separate tables will be prepared for the following:

- TEAEs by phase (treatment/rescue) and overall
- TEAEs related to IBSM inoculum
- TEAEs related to treatment
- TEAEs related to rescue drug

Additionally, a summary table by MedDRA preferred term will show the number and percentage of subjects with at least one event, by descending order of frequency (number of subjects with events in the total group). This table will be shown by phase (treatment/rescue) and overall. Treatment phase is defined as Day 8 after dosing or earlier to Day 42±2 (OZ439 and PQP) and rescue phase from Day 42±2 after dosing (Rescue treatment) to (EOS visit).

Prior and concomitant medications

Prior and concomitant medications relative to inoculum and IP will be listed for each subject and coded using the WHO drug dictionary (latest version available to CNS) with the listing to include the verbatim term and WHO drug dictionary drug class and preferred term (anatomical therapeutic chemical (ATC) Level 2 and standardised medication name), where appropriate. Prior medications relative to inoculum will be defined as those medications started before the administration of Inoculum (Day 0) and prior medications relative to IP will be defined as those medications started before the administration of IP (Day 8).

Concomitant medications relative to inoculum will be defined as those medications started on or after the administration of inoculum (Day 0) up to the EOS visit or premature study withdrawal, whichever is earliest and concomitant medications

	
STATISTICAL ANALYSIS PLAN
	
QP17C19

		
Page 23 of 53

relative to IP will be defined as those medications started on or after the administration of IP (Day 8) up to the EOS visit or premature study withdrawal, whichever is earliest.

Medications with a start date/time prior to administration of inoculum and an end date/time after administration of the inoculum will be assigned to both prior medication and concomitant medication categories relative to inoculum.

Medications with a start date/time prior to the administration of IP and an end date/time after administration of IP will be assigned to both prior medication and concomitant medication categories relative to IP.

Laboratory parameters

All individual laboratory results (haematology, biochemistry, and urinalysis) and change from baseline values will be presented in data listings. Values outside the laboratory reference range will be flagged (low-L, high-H). Classification will be done in standardised units, using non imputed values and limits. In addition, abnormal haematology, biochemistry and urinalysis laboratory parameters considered clinically significant will be presented in a listing with all parameters listed in a single column. All laboratory data will be listed. In addition, a listing will be provided showing only parameters for which abnormal values were reported.

Additionally, for liver enzymes, the following elevation categories will be defined:

- ALT: >3 x Upper Limit of Normal (ULN); >5 x ULN; >8 x ULN
- AST: >3 x Upper Limit of Normal (ULN); >5 x ULN; >8 x ULN
- ALT or AST >3 x ULN;
- Total bilirubin >2 x ULN;
- ALT or AST >3 x ULN and total bilirubin >2 x ULN at the same time point, together with a conjugated bilirubin fraction (direct bilirubin / total bilirubin) > 35% (Potential Hy's law cases).

The statistical analysis will present results in standardised units.

Continuous laboratory parameters will be summarised by means of descriptive statistics at each analysis visit. Actual values and changes from baseline will be tabulated separately. Categorical and semi-quantitative parameters will be listed only.

Laboratory abnormalities will be presented as cross-tabulations of the abnormality at each post-baseline analysis visit versus the baseline abnormality. Numbers of subjects with treatment-emergent abnormalities will also be shown.

Additionally, a frequency table showing the liver enzyme elevation categories for the highest post-dose values will be prepared.

Vital signs

The following vital signs parameters are collected: supine heart rate, supine systolic (SBP) and diastolic blood pressure (DBP) and body temperature.

Low, normal, and high ranges for vital signs are defined in Table 5 below.

Table 5. Low, normal, and high ranges for vital signs

	Heart rate (bpm)	SBP (mmHg)	DBP (mmHg)	Temperature (°C)
Low	<40	<90	<45	<35.0
Normal	40-100	90-150	45-90	35.0-37.5
High	>100	>150	>90	>37.5

Vital signs parameters will be summarised by means of descriptive statistics at each analysis visit. Actual values and changes from baseline will be tabulated separately.

Abnormalities will be presented as cross-tabulations of the abnormality at each post-baseline analysis visit versus the baseline abnormality. Numbers of subjects with treatment-emergent abnormalities will also be shown.

All vital signs data will be listed. In addition, a listing will be provided showing only abnormal values and their baseline.

Electrocardiograms

All individual ECG parameter results (heart rate, PR interval, RR interval, QRS duration, QT interval, QTcB interval, QTcF interval) and the clinical assessment of the ECG will be presented in a data listing. ECG parameter values and changes from baseline will be summarised, using descriptive statistics, by treatment and visit. Where triplicate ECG evaluations were performed, the mean value for each subject (for the protocol specified time-point) will be used for the calculation of summary statistics. In addition, individual abnormal ECG results will be presented in a separate data listing.

The clinical assessment of the ECG (RR, PR, QRS, QT and QTcF intervals) will be presented in subject data listings.

Clinical assessment of the ECG (Normal, Abnormal NCS, Abnormal CS, Not Evaluable and Not Done) will also be summarized, by treatment, using frequency tabulations (number and percentage of subjects under each category). The normal ECG ranges once on study are in Table 6.

Table 6. ECG normal ranges

Parameter	Range
PR interval	<= to 210 msec
QRS	>50 to < = to 120 msec
QT interval	>200 to < 500 msec
QTcB/QTcF	Males: ≤ 450 msec
QTcB/QTcF	Females: ≤ 470s msec

Malaria clinical score

For each subject, malaria clinical score will be listed as individual score for each of the 14 symptoms. The total of all the scores obtained on the 14 symptoms will also be presented, per timepoint. The number (and percentage) of subjects scoring each symptom (0=absent; 1=mild; 2=moderate; 3=severe) will be tabulated per treatment and per protocol defined timepoint. In addition, the total malaria clinical score will be treated as a continuous outcome and summarised per treatment and over timepoint, as well as a change from baseline, using descriptive statistics.

Physical examinations

Abnormal physical examination assessment findings will be listed.

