## 2.2 RATIONALE

This study aims to evaluate the antimalarial activity of co-administered single doses of OZ439 and PQP in the IBSM model, and enable characterisation of the exposure-response relationship between OZ439 and PQP PK and blood stage asexual parasitaemia. Previous research has shown that the IBSM model is a good predictive model for real world antimalarial drug activity with single drug administration [7]. However, it is yet to be determined if the model is an effective predictive tool when two or more drugs are administered in combination.

We hypothesise that data obtained in a controlled disease-like setting (Phase 1 drug combination IBSM model) can be used to effectively predict the outcome of Phase 2 studies in patients with uncomplicated malaria. To evaluate this hypothesis, we will assess if the outcome of this trial can be used to predict what was observed in patients with uncomplicated malaria in the MMV\_OZ439\_13\_003 Phase 2b combination trial [8].

The doses chosen for use in Cohort 1 are based on the PK/PD relationships from the IBSM monotherapy studies and potential PD interaction effects of the combination based on the phase IIb study. Several doses will be tested in Cohort 1, which should achieve parasite reduction but not complete cure, such that parasite regrowth can be observed, allowing an initial estimation of the PK/PD parameters of the 2 drugs when combined. The results of the first cohort will then be used to guide dose selection for Cohort 2 and maximising the information on the PD interaction effect.

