### 7.3.7 SCHEDULE OF EVENTS TABLE

The Schedule of Events Table summarises the procedures to be conducted as per this protocol during screening, confinement and postconfinement. Section 7.1 and 7.2 provide detailed information on the procedures.

An experienced nurse will be in attendance at the clinical unit when subjects are on site and the Investigator will be available within approximately 30 minutes call back if required.

In the schedule of events, evaluation may be in the morning, between 6:00 AM to 11:00 AM, and in the afternoon, between 6:00 PM to 11:00 PM, therefore separated by approximately 12

Some safety and laboratory evaluation days may vary  $\pm 2$  days based on qPCR counts and clinical unit visits at the investigator's discretion.

Table 2: Schedule of Events

Procedure	Screening D-28 to D-1	Eligibility visit a D-3 to D-1	Malaria inoculation day D0	Post- inoculation phone contact D1 to D3	Malaria monitoring b D4 to D7	OZ439 and PQP treatment and clinical unit confinement D8 to D11	Out-patient monitoring D12 to D42±2	Rescue treatment with Riamet® D42±2 or earlier if required	EOS visit D45±2
Informed consent & BDI	X								
Medical history, eligibility & prior medications	X		X						
Drug & alcohol screen	X		X			X			
Full physical examination	X								X
Abbreviated physical examination			X			X r			
Symptom-directed physical examination					X	X	X	X	
Vital sign assessment	X		X		X	X	X	X	X
ECG	X		X			X i		X	X
Urinalysis	X	X				X k	X		X
Haematology & biochemistry	X	X				X	X	X	X
Coagulation profile e	X								
G6PD testing	X								
RBC alloantibody	X								X
Serology	X								X
Serum β-hCG pregnancy test	X d	X							X
Urine β-hCG pregnancy test			X			X			
Safety serum storage			X						X
AEs & concomitant medications			X	X	X	X	X	X	X
Malaria clinical score			X		X	X	X l	X	X
Malaria 18S qPCR blood sampling			X		X	X	X m	X	X
Parasite lifecycle stage qPCR blood sampling							X	X	X
OZ439 and PQP concentration blood sampling						X	X	X s	
Phone call or text message								X n	
Malaria inoculum			X g						
OZ439 and PQP treatment						X			
Riamet® treatment								X	
Primacin™ treatment l								X	

Immune cell characterisation (optional)			X o		X p	X q	X		X
Complement regulatory proteins (optional)			X o			X q	X		X

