#### 10.3.4 SAFETY ANALYSES

The overall number and percentage of subjects with at least one AE (and SAE) will be tabulated over the entire study period. All AE data will be summarised by pooled treatment group and study period, i.e. Day 0 to Day 8 (inoculum), Day 8 after dosing or earlier to Day 42 (OZ439 and PQP) and Day 42+2 after dosing (Rescue treatment) to (EOS visit).

Treatment emergent AE's will also be summarised with frequency counts by MedDRA system organ class (SOC; i.e. body system) and preferred term (PT), for each pooled treatment group and by Study period.

Vital signs, routine safety laboratory data and ECG parameters will be presented in data listing and will be summarised descriptively by treatment group and by protocol specified time point.

Where applicable, both absolute values and change from baseline (inoculation and IMPs administration) will be presented and listings of clinically relevant abnormal laboratory results will be generated.

The safety and tolerability of a single combined dose of OZ439 and PQP will be evaluated by the incidence, severity and relationship of observed and reported AEs up to trial Day 42.

---

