Subjects then came to the clinical unit once daily from Day 4 until presence of asexual parasites was established by quantitative polymerase chain reaction (qPCR) targeting the 18S rRNA gene (referred to hereafter as malaria 18S qPCR). Once malaria 18S qPCR became positive and until OZ439 and PQP administration, subjects came to the clinical unit twice-daily, separated by approximately 12 hours, for clinical evaluation and blood sampling.

On day 8, subjects were admitted to the clinical unit for single dose administration of OZ439 and PQP on Day 8. Subjects were followed up as inpatients for 72 hours to ensure tolerance of the investigational treatments (OZ439 and PQP) and clinical response.

After discharge from the clinical unit, subjects were followed up regularly for safety assessments, PK sampling, clinical evaluation, and malaria 18S qPCR blood sampling until Day 42±2 (34 days after OZ439 and PQP co-administration). All subjects received a standard course of Riamet® (artemether-lumefantrine) on Day 42±2, or earlier in the event of failure of clearance or recrudescence of parasitaemia or at Investigators discretion based on subject safety. For guidance, the definitions for failure of parasite clearance and recrudescence are provided.

- **Failure of parasite clearance:** failure to clear parasitaemia by at least 10-fold at 72 hours post-IP administration
- **Recrudescence:** defined as participants who showed substantial increases in parasitaemia after the initial clearance and were treated with a standard course of Riamet® to clear parasites.

The clinical judgement was made based on serial samples to ensure participant safety. Guidelines for increasing parasitaemia following initial clearance were a 2-fold parasitaemia increase from previous sample and parasitaemia exceeding the

	STATISTICAL ANALYSIS PLAN	QP17C19
		Page 12 of 53

clinically safe threshold (e.g. ≥ 5000 blood stage parasites/mL), or re-occurrence of malaria symptoms with a malaria clinical score >6 . However clinical judgement and practicality were overriding criteria for rescue treatment.

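### The by-phase TEAE tables switch to rescue at Day 42±2, so adverse events after an earlier rescue dose are tabulated under OZ439/PQP treatment

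*SAP*

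**What the plan says.** SAP 6.8 plans TEAE tables by phase (treatment or rescue) and overall, by system organ class and preferred term and also by preferred term in order of frequency. It gives the limits as follows: "Treatment phase is defined as Day 8 after dosing or earlier to Day 42±2 (OZ439 and PQP"), and then "rescue phase from Day 42±2 after dosing (Rescue treatment) to (EOS visit"). Protocol 10.3.4 summarises adverse events by the same study periods: "Day 8 after dosing or earlier to Day 42 (OZ439 and PQP) and Day 42+2 after dosing (Rescue treatment) to (EOS visit").

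Rescue itself is not tied to Day 42. SAP 2.1 has Riamet given "on Day 42±2, or earlier in the event of failure of clearance or recrudescence of parasitaemia", or at the investigator's discretion. The rescue column of the protocol's Schedule of Events (7.3.7) is headed "D42±2 or earlier if required". Under Recrudescence, SAP 8.4 defines a recrudescent subject partly by Riamet given before the scheduled compulsory time.

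Early rescue is also expected from the design. Protocol 2.2 says that several doses were chosen for Cohort 1 "which should achieve parasite reduction but not complete cure, such that parasite regrowth can be observed".

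**The concern.** The phase labels name exposures: OZ439 and PQP for one, rescue treatment for the other. A reader of the tables will take the treatment column as events before any rescue drug. In both definitions, the allowance for an earlier date is attached to the start of the treatment phase, that is, to early dosing with OZ439/PQP. Nothing comparable is attached to the start of the rescue phase, and the SAP has no rule that moves events following an early rescue.

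For a subject rescued early, events arising during or after Riamet (and Primacin or artesunate, if used) would therefore appear in the OZ439/PQP column. The same subject's rescue column would cover only about Day 42 to the end-of-study visit on Day 45±2, when the Riamet course may have finished long before. What is at stake is whether the by-phase tables show what their labels say.

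**Working it through.** The plan states no figure to reproduce. The check compares the definitions and then uses day arithmetic.

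**Definitions side by side**

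| Item | Boundary | Source |
|---|---|---|
| End of treatment phase, start of rescue phase | Day 42±2 | SAP 6.8; same boundary in protocol 10.3.4 |
| Actual first rescue dose | Day 42±2 or earlier | SAP 2.1; protocol 7.3.3 and 7.3.7 |

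The two agree for subjects rescued on Day 42±2. They differ for everyone rescued earlier.

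**Inputs**

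- OZ439/PQP dosing on Day 8, so the nominal treatment phase is 42 − 8 = 34 days. SAP 2.1 gives the same 34 days.
- Earliest guideline trigger for rescue: failure of clearance at 72 hours after dosing (SAP 2.1), which is Day 11. Investigator discretion could be earlier.
- Riamet course: 60 hours (protocol 6.1.5), which is 60/24 = 2.5 days.
- Rescue day r for early-rescued subjects: not in the documents. The values below are assumptions.

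**Formula.** Treatment-phase days that fall after rescue = 42 − r; share = (42 − r)/34.

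| Assumed rescue day r | 42 − r | Share of 34 days |
|---|---|---|
| 11 | 31 | 91% |
| 15 | 27 | 79% |
| 25 | 17 | 50% |
| 35 | 7 | 21% |

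The ±2 window on the boundary moves each count of days by 2 either way; for Day 11 the range is 29 to 33 days.

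A Riamet course started by Day 42 − 2.5 = 39.5 lies wholly inside the nominal treatment phase.

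**Group level.** In a dose group of 4 with 2 subjects rescued on Day 25, the post-rescue share of treatment-phase person-days is (2 × 17)/(4 × 34) = 34/136 = 25%. If all 4 are rescued on Day 25 it is 50%.

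**After the change.** With the boundary at each subject's first rescue dose, the post-rescue days in the treatment phase fall from 42 − r to 0. The split is essentially unchanged for subjects rescued on Day 42±2.

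These are shares of time at risk. They are not shares of misplaced events, because events need not be spread evenly over follow-up.

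**The case against.** **The wording may already mean the rescue dose.** The rescue phase is described as after dosing with rescue treatment, which parallels the wording for Day 8. SAP 6.3 lists rescue treatment as a time point separate from outpatient monitoring. A programmer could anchor the phase on the actual dose. This stands as evidence of intent, and it supports the correction: the only boundary written down is Day 42±2, which is also not an exact date.

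**The effect on safety conclusions is limited.** This stands. A reader might infer that the co-primary adverse event endpoint is wrong. It is not: protocol 4.2.1 counts events up to Day 42 and SAP 2.3 counts events after dosing, neither with a cut at rescue. SAP 6.8 also plans overall TEAE tables and separate tables for events related to treatment, to inoculum and to rescue drug, none of which depends on phase. The table titles in SAP Appendix 2 do not mention phase.

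**PQP is still present after an early rescue.** Its half-life is 4 to 5 weeks (protocol 2.1), and PK sampling continues on schedule after early Riamet (Schedule of Events footnotes). A per-subject cut would move some events that occur under PQP exposure into the rescue phase. That is true, but it is a small cost. The 34 days to Day 42 are only about one such half-life (34/35 = 0.97 to 34/28 = 1.21), so subjects rescued at Day 42 also still carry PQP and are already moved at that point. A per-subject cut applies the plan's own split consistently, and the overall and causality tables still show every such event.

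**The PK/PD dataset is not a precedent for safety data.** SAP 9.3 flags parasite data after the first rescue dose but states no such cut for drug concentrations. This stands, and the point does not rely on it.

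**Conclusion.** The definition should be corrected. As written, it places adverse events that start after an early rescue dose in the OZ439/PQP phase, and it can leave an early-rescued subject with a rescue phase that contains no rescue dosing. The reach is confined to the by-phase descriptive tables.

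The size depends on how many subjects were rescued early and when, which the documents do not say. For rescue between Day 11 and Day 35, an assumed range, 91% to 21% of that subject's nominal treatment phase is post-rescue time.

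Two stronger readings are tempting and are not supported:

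- A reader might infer that the error is largest at low doses and so biases comparisons of event rates between dose groups. Protocol 2.2 describes the Cohort 1 doses collectively, and neither document reports rescue frequency by dose. Protocol 10.1 says the study is not powered to compare doses, and the safety analysis is descriptive.
- A reader might infer that one misplaced subject shifts an event percentage by 50 or 25 points in a group of 2 or 4. That happens for a given term only if the subject has the event after rescue and not earlier in the treatment phase.

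**What to change.** In SAP 6.8, define the phases per subject by actual dose times:

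- Treatment phase: from the OZ439/PQP dose to just before the first dose of any rescue drug.
- Rescue phase: from the first rescue dose, whether on Day 42±2 or earlier, to the end-of-study visit.

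Apply this to every by-phase table, leave the overall TEAE tables unchanged, and align the study periods in protocol 10.3.4. Reporting events per days at risk in each phase would be an optional addition.

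The cost is a wording change and one derived variable. Protocol 8.4.1 already has event onset recorded relative to the rescue drugs, and SAP 6.7 already lists the date and time of rescue dosing. SAP 6.3 currently derives event times only from inoculum and from study treatment, so time since first rescue dose should be added there. Data collection and clinical management do not change. The downside is the one noted above: some events under continuing PQP exposure move to the rescue phase, so a table footnote should say so.

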### Vital signs

Vital signs (temperature, heart rate, respiratory rate and blood pressure) will be measured at screening after the subject has rested in the supine position for at least 5 minutes and in the standing position within 23 minutes when changing from the supine to standing position (blood pressure and heart rate only). At all other time points, vital signs will be measured after the subject has rested in the seated position for at least 5 minutes. Tympanic temperature will be taken at the clinical unit

The normal ranges for vital signs on study are:

Parameter	Range
Systolic blood pressure	90-140mmHg
Diastolic blood pressure	50-90 mmHg
Heart rate	50 -100 bpm
Temperature	35.0-37.5°C
Respiratory rate	10-25 breaths/min
Peripheral O2 Saturation	>=95%

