6.1 GENERAL CONSIDERATIONS

The statistical analysis and reporting of safety data will be the responsibility of the study biostatistician at CNS. Data will be reported for the inoculation set and/or for the safety set as relevant.

For categorical/discrete variables, the population size (N for sample size and n for available data) and the percentage (of available data) for each class of the variable will be presented. Continuous variables will be summarised using descriptive statistics, including n, mean, standard deviation (SD), median, minimum, and maximum values.

Numeric safety variables (i.e. clinical laboratory values, vital signs, and key ECG parameters) will be reported to the same precision as the source data. Derived variables will be reported using the same precision to the value(s) from which they were derived. For the reporting of descriptive statistics, the minimum and maximum values will be presented to the same precision as the source data; mean and median will be reported to 1 decimal place greater than the source data and SD will be reported to 2 decimal places greater than the source data. The coefficient of variation (%CV) will always be reported as a percentage (i.e. $\times 100$) to 1 decimal place.

Extra measurements (such as unscheduled or repeat assessments) will not generally be included in summary tables, but will be included in subject listings.

For safety data, unless specifically mentioned otherwise, baseline is defined as:

- the last scheduled observation prior to the administration of the inoculum [Inoculation Baseline],
- the last scheduled observation prior to the first administration of IP(s) [Treatment Baseline].

	
STATISTICAL ANALYSIS PLAN
	
QP17C19

		
Page 18 of 53

If a scheduled baseline reading is missing, then the last non-missing measurement (e.g. screen value or unscheduled) will be used.

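### SAP Table 5 classes as normal some heart rate and blood pressure readings that fall outside the protocol's on-study ranges, and section 6.8 calls seated readings supine and omits respiratory rate

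*SAP*

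**What the plan says.** Protocol section 7.1.1, under Vital signs, tabulates normal ranges that apply on study. They include "Systolic blood pressure 90-140mmHg" and "Heart rate 50 -100 bpm", with diastolic pressure 50–90 mmHg, temperature 35.0–37.5 °C and respiratory rate 10–25 breaths/min. The vital signs it lists as measured are temperature, heart rate, respiratory rate and blood pressure. At screening they are taken supine, with blood pressure and heart rate repeated standing. After that: "At all other time points, vital signs will be measured after the subject has rested in the seated position for at least 5 minutes".

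SAP section 6.8 describes the data differently: "The following vital signs parameters are collected: supine heart rate, supine systolic (SBP) and diastolic blood pressure (DBP) and body temperature". It then says: "Low, normal, and high ranges for vital signs are defined in Table 5 below". The middle row of that table, in the order heart rate, systolic, diastolic, temperature, reads "Normal 40-100 90-150 45-90 35.0-37.5".

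These classes feed the tabulations: "Abnormalities will be presented as cross-tabulations of the abnormality at each post-baseline analysis visit versus the baseline abnormality". The same section also plans counts of subjects with treatment-emergent abnormalities and a listing restricted to abnormal values.

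For missing baselines, SAP section 6.1 provides: "If a scheduled baseline reading is missing, then the last non-missing measurement (e.g. screen value or unscheduled) will be used". SAP section 1.1 says that SAP analyses prevail where they differ from the protocol.

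**The concern.** The two documents give different meanings to a normal vital sign, and the SAP does not acknowledge the difference. A reader of the study report who takes the protocol's ranges as the standard will find readings outside them tabulated as normal.

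The categorical tables matter here because other routes may not pick these readings up. Protocol section 8.1.1 asks that borderline objective findings not be routinely reported as adverse events, because they are to be analysed separately; the vital-sign tables are part of that separate analysis. Both documents exclude asymptomatic sinus bradycardia without other relevant ECG abnormality from the events of special interest, and SAP Table 6 (ECG ranges) has no heart-rate limit. An asymptomatic heart rate in the 40s could therefore appear in no abnormality count. Protocol section 2.3.1 mentions one mild, reversible case of sinus bradycardia among malaria patients treated with OZ439.

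The position label is a separate matter of fact. Output headed supine would misdescribe almost all the data in it.

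**Working it through.** No sample-size, power or error-rate figure is involved. The check is to classify every integer value under both sets of limits and list those that differ.

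Inputs: on-study ranges from protocol 7.1.1, analysis limits from SAP Table 5, entry limits (supine) from protocol 5.1, criterion 4.

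| Parameter | Protocol on study | SAP Table 5 normal | Protocol entry | Outside protocol range, normal in SAP | Reverse |
|---|---|---|---|---|---|
| Heart rate (bpm) | 50–100 | 40–100 | 40–100 | 40–49 (10 integer values) | none |
| Systolic (mmHg) | 90–140 | 90–150 | 90–140 | 141–150 (10 values) | none |
| Diastolic (mmHg) | 50–90 | 45–90 | 40–90 | 45–49 (5 values) | none |
| Temperature (°C, steps of 0.1) | 35.0–37.5 | 35.0–37.5 | not given | none | none |

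Step 1. Three limits differ: heart rate lower, diastolic lower, systolic upper. Each is wider in the SAP. The other limits agree: heart rate upper 100, systolic lower 90, diastolic upper 90, and both temperature limits.

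Step 2. Heart rate below 40, diastolic below 45 and systolic above 150 are abnormal under both documents, so the gap is confined to the three bands shown.

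Step 3. Do the entry criteria explain Table 5? Only for heart rate, where the range is identical. The SAP diastolic range (45–90) and systolic range (90–150) match neither the on-study nor the entry range.

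Step 4. What would change at baseline? Under the protocol's on-study ranges, a subject could meet the entry criteria with a heart rate of 40–49 or a diastolic pressure of 40–49 and be classed low. Under Table 5, that already happens for diastolic 40–44. Aligning the limits can only raise the number of readings classed abnormal. Treatment-emergent counts need not all rise: if such an abnormality means one absent at baseline (the SAP does not define it for vital signs), a subject at 40–49 bpm at baseline who later falls below 40 would stop counting.

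Step 5. Position. In the protocol, only screening is supine; every later reading is seated. The SAP label is therefore wrong for all post-screening heart rate and blood pressure values.

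Step 6. Baseline fallback. Protocol 7.3 schedules vital signs on Day 0 before inoculation, at each visit from Day 4, and at Day 8 admission. Because the fallback takes the last available value, a missing Day 8 reading would normally be replaced by a seated one from Days 4–7. A supine screening value would be reached mainly if the Day 0 reading before inoculation were missing.

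**The case against.** The best defence is that SAP 1.1 lets the SAP depart from the protocol, and that a lower heart-rate limit of 40 avoids labelling eligible subjects abnormal at baseline. That is a fair reason for one limit. It does not explain the diastolic or systolic limits, and the SAP does not state it. Precedence also cannot change the position in which a reading was taken.

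A second defence is that little is lost. All vital signs are listed, descriptive statistics and changes from baseline do not use Table 5, ECG heart rate is summarised separately, and clinically significant findings become adverse events. This stands, and it keeps the point small.

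Several stronger readings are tempting but unsupported:

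- A reader might infer an oversight, because protocol version 4.0 added the ECG and vital-sign ranges together and the SAP reproduces only the ECG ones. That is suggestive, but the documents do not settle intent.
- A reader might infer that orthostatic hypotension, a listed risk, will be under-reported. The lower systolic limit is 90 in both documents, and standing readings are taken only at screening, so these limits could not detect it.
- A reader might expect the tables to conflict with flags set at the site. The version history mentions alignment with eCRF guidelines, but no vital-sign flag is described. The outpatient malaria score may also be taken at the investigator's discretion.
- A reader might want the share of readings affected. The documents give no vital-sign distributions, so any percentage would rest on assumed means and SDs.
- A reader might count missing oxygen saturation as an error. The protocol gives a range for it but neither lists it among the measured vital signs nor schedules it.
- A reader might infer that change from baseline routinely mixes supine and seated values. Step 6 shows that this should be rare.

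**Conclusion.** The inconsistency is real and minor. Readings in three bands (heart rate 40–49 bpm, diastolic 45–49 mmHg, systolic 141–150 mmHg) lie outside the protocol's on-study ranges and will be tabulated as normal, with no reason given. The supine label is wrong after screening, and respiratory rate is measured but missing from the SAP.

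The consequence is limited to the vital-sign cross-tabulations, treatment-emergent counts and abnormal-only listing, plus the description of the data. PK/PD and parasite clearance results are untouched. Dose groups hold 2 or 4 subjects, so one reclassified subject would move a group's figure by 1/2 = 50 or 1/4 = 25 percentage points. How often that would happen cannot be derived from the documents.

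The conclusion assumes that the protocol's on-study ranges are meant to define normal for reporting. Their heading supports this, but the protocol does not say expressly that they govern the analysis.

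**What to change.** Reconcile the two documents in SAP section 6.8:

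1. Set the Table 5 analysis limits to the on-study ranges in protocol 7.1.1, or state in the SAP why they differ.
2. Add respiratory rate to the list of parameters and to Table 5.
3. Describe heart rate and blood pressure after screening as seated.
4. As a minor safeguard, bar a supine screening value from serving as the fallback baseline for seated heart rate and blood pressure. Use the last seated value before the relevant administration, or set the change to missing.

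The cost is a table edit and a rerun of the vital-sign outputs. More readings will be flagged, some at baseline because entry allows heart rate and diastolic pressure down to 40. The planned cross-tabulation against baseline already shows those.
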